2.4. Statistical Hypotheses

The study is to determine the effect of GSK1070806 on DGF. Stopping rules have been defined to test whether the DGF rate is less than or equal to the null hypothesis rate of 50%.

2.5. Definition of Renal Graft Function

Primary Non Function:

- Permanent lack of function of the allograft defined as an inability to discontinue dialysis from the time of transplantation. Note: The study site will decide whether patients have primary non function DGF or not and record it in data set.

3 day Functional Delayed Graft Function:

- <10% fall in SCr versus baseline per day averaged over first 3 days with OR without dialysis

7 day Functional Delayed Graft Function:

- <30% reduction in baseline SCr in first 7 days with OR without dialysis

3 day Intermediate Graft Function:

- 10- 20% fall in SCr versus baseline per day averaged over first 3 days without dialysis

7 day Intermediate Graft Function:

- 30-70% reduction in baseline Cr in first 7 days without dialysis

3 day Immediate Graft Function:

- >20% fall in SCr versus baseline per day averaged over first 3 days without dialysis

7 day Immediate Graft Function:

- >70% reduction in baseline Cr during the first 7 days without dialysis

3. PLANNED ANALYSES

3.1. Interim Analyses

3.1.1 Bayesian Sequential Analysis

The DGF data will be reviewed sequentially. The sequential decision rule is shown graphically in Figure 1. The number in the first column indicates the number of subjects who have completed study treatment. From the point in time when approximately 6 subjects have reached day 7 post transplantation the sponsor study team will begin to evaluate the DGF rates. This will start with the first 6 subjects and then with addition of data from each subsequent subject that completes 7 days of the trial. A sequential Go/No Go/Continue rule is based on the predictive probability of success. A high predictive probability (PP) of success means that GSK1070806 is likely to be efficacious by the end of the study given the observed data, whereas a low PP suggests that the treatment may not have sufficient activity. If the PP value is less than 2% (red region) the trial may be stopped and the alternative hypothesis will be rejected. If the PP is greater 92% (green), the conclusion may be made that GSK1070806 has better efficacy than the standard of care. If the PP is between 2 - 92% (white region), the trial will continue to the next interim analysis (to be conducted after the next subject has completed treatment) or until reaching 30 completed subjects.

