1. REPORTING & ANALYSIS PLAN SYNOPSIS

Overview	Key Elements of the RAP
Purpose	
 This RAP details all planned analyses and outputs required for the final Clinical Study Report (CSR) of study 204824.
Protocol	
 This RAP is based on the protocol (Dated: 03-FEB-2016 for study 204824 [GlaxoSmithKline Document Number: 2015N240632_01]).
Primary Objective	
 Evaluate the efficacy of single intravenous dose administrations of GSK1070806 in prevention of delayed graft function (DGF) after transplantation.
Primary Endpoint	
 Proportion of subjects requiring dialysis during the first 7 days post transplant (excluding requirement for dialysis due to hyperkalemia within first 24 post-operative hours).
Study Design	
 Pilot, multicenter, single arm Bayesian sequential design study to evaluate the efficacy, safety, tolerability and pharmacokinetics (PK) of GSK1070806 in patients undergoing renal transplantation. Sample size (maximum of 30) had been selected to yield the probability of a “go” decision of 0.139 when the GSK1070806 DGF rate is 50% and 0.69 at what has been considered to be a clinically impactful GSK1070806 DGF rate of 35%.
Planned Analyses	
 Interim analyses are detailed within Section 3.1 where applicable. All decisions regarding final analysis, as defined in this RAP document, will be made prior to Database Freeze of the study data.
Primary Analysis Population	
 The ‘Analysis Population’ will be used to evaluate DGF related endpoints The ‘All Subjects Population’ will be used to evaluate study population; safety; PD/Biomarkers and other efficacy endpoints. The ‘PK’ population will be used to evaluate pharmacokinetics. The ‘Per-Protocol’ population will be used to evaluate the DGF rate in addition to the ‘Analysis Population’.
Hypothesis	
 The study is to determine the effect of GSK1070806 on DGF. Stopping rules have been defined to test whether the DGF rate is less than or equal to the null hypothesis rate of 50%.
Primary Analyses	
 A summary of the observed DGF rate during the study will be provided. The posterior probability that the proportion of subjects experiencing DGF is less than 50% will be calculated.

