3.2. Final Analyses

A summary of the observed DGF rate during the study will be provided. The posterior probability that the proportion of subjects experiencing DGF is less than 50% will be calculated.

Figure 1

Sequential Decision Rules

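### SAP 3.1.1 treats a predictive probability below 2% as rejecting the alternative, although at late No-Go results the plan's own posterior can still favour a DGF rate below 50%

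*SAP*

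**What the plan says.** Section 3.1.1 sets a Go/No-Go/Continue rule on the predictive probability of success. On reviewing the data it says: "This will start with the first 6 subjects and then with addition of data from each subsequent subject that completes 7 days of the trial". Continuation runs to the next subject "or until reaching 30 completed subjects". The two conclusions are:

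- Go: "If the PP is greater 92% (green), the conclusion may be made that GSK1070806 has better efficacy than the standard of care".
- No-Go: "If the PP value is less than 2% (red region) the trial may be stopped and the alternative hypothesis will be rejected".

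In the No-Go sentence stopping is optional, but rejection of the alternative is not. Slightly earlier, the same section describes a low PP more cautiously, as a sign that activity may be insufficient.

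Section 2.4 gives the hypothesis in one sentence: "Stopping rules have been defined to test whether the DGF rate is less than or equal to the null hypothesis rate of 50" per cent. It does not state the alternative separately. Section 3.2 plans the evidence measure for the final analysis: "The posterior probability that the proportion of subjects experiencing DGF is less than 50% will be calculated". The synopsis gives a Go probability of 0.139 at a DGF rate of 50% and "0.69 at what has been considered to be a clinically impactful GSK1070806 DGF rate of 35" per cent.

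**The concern.** PP is the chance, given the data so far, of finishing with a result that counts as success. A low value means that a demanding bar will probably be missed. It does not mean that the DGF rate is 50% or more. The plan nevertheless moves from the first statement to a hypothesis decision, and it also plans to report the posterior probability that the rate is below 50% from the same data. In the late part of the grid the two can point in opposite directions. The study report could then say that the alternative was rejected and, alongside, that it is more likely than not, or even about 92% probable. In a single-arm pilot of at most 30 subjects, used for an internal decision, that would present a missed threshold as evidence against the drug.

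**Working it through.** **Inputs.** Looks after every subject from 6 to 30, Go if PP > 0.92 and No-Go if PP < 0.02 (3.1.1); the PP grid (Figure 1); reference rate 50% (2.4, 3.2); Go probabilities 0.139 and 0.69 (synopsis).

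**Success criterion.** In the row for 30 subjects, PP is 1 at 11 events and 0 at 12. Success is therefore 11 or fewer events in 30.

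**Prior.** The SAP does not state one, so it has to be inferred. With prior Beta(a,b), n subjects and x events,

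PP(n,x) = P(future events ≤ 11 − x), future events ~ beta-binomial(30 − n; a + x, b + n − x).

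With a = 5 and b = 8 this matches all 325 printed cells; the largest difference is 0.0005, which is rounding. Examples: 0/0 gives 0.515, 3/6 gives 0.339, 8/20 gives 0.415 and 11/29 gives 0.619, all as printed.

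**The plan's own figures.** Exact forward recursion over (n,x), with every boundary crossing taken as a stop:

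| True DGF rate | P(Go), computed | P(Go), stated | P(No-Go) |
|---|---|---|---|
| 50% | 0.1389 | 0.139 | 0.861 |
| 35% | 0.6895 | 0.69 | 0.310 |

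Both stated figures reproduce. Every path ends in Go or No-Go, so the last column is one minus the second.

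**Posterior at the No-Go cells that can be reached first.** P(DGF<50%) is the Beta(5 + x, 8 + n − x) distribution function at 0.5. The flat-prior version uses Beta(1 + x, 1 + n − x).

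| Events/subjects | Inferred Beta(5,8) | Flat prior |
|---|---|---|
| 6/6 | 0.24 | 0.01 |
| 8/12 | 0.42 | 0.13 |
| 9/14 | 0.42 | 0.15 |
| 9/15 | 0.50 | 0.23 |
| 10/17 | 0.50 | 0.24 |
| 10/18 | 0.57 | 0.32 |
| 11/20 | 0.57 | 0.33 |
| 11/21 | 0.64 | 0.42 |
| 11/22 | 0.70 | 0.50 |
| 12/24 | 0.69 | 0.50 |
| 12/25 | 0.74 | 0.58 |
| 12/26 | 0.79 | 0.65 |
| 12/27 | 0.83 | 0.71 |
| 12/28 | 0.87 | 0.77 |
| 12/29 | 0.89 | 0.82 |
| 12/30 | 0.92 | 0.86 |

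The early cells not shown (6/7, 7/9, 8/11) lie between 0.32 and 0.34 under Beta(5,8).

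**How often the conflict would arise.** Given a No-Go at a true rate of 35%, the posterior is above 0.5 in 0.251/0.310 = 81% of outcomes under Beta(5,8) and in 0.177/0.310 = 57% under a flat prior. It is above 0.8 in 42% and 21% respectively. The exact ties at 9/15 and 10/17 are not counted.

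**The sharpest contrast.** Under Beta(5,8), 11/30 has posterior 0.956 and is a success, while 12/30 has 0.918 and would reject the alternative. One event reverses the conclusion while the posterior falls by 0.038.

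**The case against.** Five points can be made for the plan.

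1. **The alternative is never defined.** If it meant the 35% target, the conflict disappears: under Beta(5,8), P(DGF<35%) is between 0.02 and 0.28 at every first-reached No-Go cell. This stands as a condition on the finding. But 50% is the only rate named in 2.4 and the only one for which 3.2 plans a posterior, so below 50% is the natural reading. The uncertainty is itself a reason to state the alternative.
2. **More likely than not is a low bar under this prior.** Beta(5,8) gives P(DGF<50%) = 0.81 before any subject is treated. At the seven late cells from 10/18 to 12/26 the posterior (0.57 to 0.79) is below that, so the data have moved against a benefit. This is correct, and only 12/27 to 12/30 end above the prior value. A move downwards to 0.6 or 0.7 is still not a rejection.
3. **The size depends on an inferred prior.** This stands, and for that reason the flat-prior results are shown beside it.
4. **Early No-Go results do count against the drug.** At 14 or fewer subjects the posterior is 0.24 to 0.42. A reader might infer that no No-Go is ever evidence of lack of benefit. The grid does not support that.
5. **The 31% No-Go rate at a true 35% is disclosed.** A reader might take it for a design error. It is 1 − 0.69, and the synopsis gives the 0.69. It is a known property of a small pilot.

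The plan is also softer elsewhere: stopping is permissive, a low PP is first described cautiously, and the posterior is planned in any case. That narrows the fault to one clause but does not remove it.

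**Conclusion.** The No-Go clause in 3.1.1 claims more than the rule can show. With the alternative read as a DGF rate below 50%, it contradicts the posterior of 3.2 at every first-reached No-Go cell from 18 subjects on under the prior inferred from Figure 1 (0.57 to 0.92), and from 25 subjects on under a flat prior (0.58 to 0.86). The result at 12/30 shows it most plainly: the alternative would be rejected at a posterior of 0.92 (flat prior 0.86).

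The finding rests on two assumptions: the reading of the alternative, and, for its extent, the prior. It does not extend to the early No-Go cells, and it is not a criticism of the boundaries, the sample size or the stated Go probabilities, which reproduce. The fault lies in the wording of an inference, and it is worth correcting because that wording would pass into the study report.

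**What to change.** In 3.1.1, replace the closing clause of the No-Go sentence so that it reads in substance: *if PP is below 2%, the trial may be stopped for futility because the success criterion (11 or fewer DGF events in 30) is unlikely to be met or can no longer be met; this alone does not reject the alternative, and the conclusion on a DGF rate below 50% rests on the reported posterior probability.* This wording leaves room for an early No-Go whose posterior favours a rate above 50% to be reported as such.

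In 2.4, state the hypotheses explicitly: null, DGF rate ≥ 50%; alternative, DGF rate < 50%. Carry the same statement into the synopsis.

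The cost is a few sentences of SAP text. No boundary, sample size, operating characteristic or planned output changes.

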3.1.2 Planned Interim Analysis

The following interim analyses are planned (protocol defined):

Interim Analysis	Details
During Study	
• The DGF data will be reviewed sequentially.• An interim analysis will be performed after recruitment of approximately 8 to 10 patients to review for a consideration of dose adjustment based on an integrated review of safety/tolerability, efficacy, and exposure.• The preliminary PK data which involves but not limited to GSK1070806 concentrations, total, free, drug bound IL-18 levels as data permit and applicable.• Once the last patient completes 7-Days post-transplant, an interim analysis will be performed of all available data for the primary endpoint in addition to supportive efficacy and safety data. The results of this interim analysis will be reviewed by the GSK study team and other relevant GSK staff for internal decision making.

3.2. Final Analyses

A summary of the observed DGF rate during the study will be provided. The posterior probability that the proportion of subjects experiencing DGF is less than 50% will be calculated.

Figure 1

Sequential Decision Rules

	# DGF Events												
	0	1	2	3	4	5	6	7	8	9	10	11	12
0	0.515												
1	0.618	0.35											
2	0.71	0.452	0.215										
3	0.788	0.553	0.3	0.119									
4	0.852	0.649	0.394	0.179	0.058								
5	0.9	0.735	0.492	0.253	0.095	0.025							
6	0.936	0.808	0.589	0.339	0.146	0.045	0.009						
7	0.961	0.867	0.68	0.433	0.21	0.074	0.018	0.003					
8	0.977	0.912	0.761	0.53	0.288	0.116	0.033	0.006	8E-04				
9	0.988	0.945	0.83	0.624	0.376	0.17	0.055	0.012	0.002	2E-04			
10	0.994	0.967	0.884	0.712	0.47	0.239	0.088	0.023	0.004	4E-04	2E-05		
11	0.997	0.982	0.926	0.79	0.567	0.32	0.133	0.039	0.008	9E-04	6E-05	1E-06	
12	0.999	0.991	0.955	0.854	0.661	0.411	0.192	0.064	0.014	0.002	1E-04	4E-06	0
13	0.999	0.996	0.975	0.905	0.747	0.508	0.265	0.1	0.025	0.004	3E-04	1E-05	0
14	1	0.998	0.987	0.942	0.821	0.606	0.351	0.148	0.043	0.008	8E-04	3E-05	0
15	1	0.999	0.994	0.967	0.881	0.7	0.447	0.212	0.069	0.014	0.002	8E-05	0
16	1	1	0.998	0.983	0.927	0.785	0.548	0.29	0.107	0.025	0.003	2E-04	0
17	1	1	0.999	0.992	0.959	0.856	0.65	0.382	0.159	0.043	0.006	4E-04	0
18	1	1	1	0.997	0.98	0.912	0.745	0.485	0.228	0.07	0.012	9E-04	0
19	1	1	1	0.999	0.991	0.951	0.828	0.593	0.314	0.109	0.022	0.002	0
20	1	1	1	1	0.997	0.977	0.895	0.7	0.415	0.165	0.038	0.004	0
21	1	1	1	1	0.999	0.991	0.944	0.798	0.529	0.24	0.063	0.007	0
22	1	1	1	1	1	0.997	0.975	0.879	0.649	0.336	0.102	0.013	0
23	1	1	1	1	1	1	0.992	0.939	0.764	0.454	0.161	0.024	0
24	1	1	1	1	1	1	0.998	0.977	0.864	0.587	0.245	0.044	0
25	1	1	1	1	1	1	1	0.995	0.939	0.725	0.359	0.077	0
26	1	1	1	1	1	1	1	1	0.984	0.854	0.505	0.134	0
27	1	1	1	1	1	1	1	1	1	0.951	0.679	0.226	0
28	1	1	1	1	1	1	1	1	1	1	0.861	0.377	0
29	1	1	1	1	1	1	1	1	1	1	1	0.619	0
30	1	1	1	1	1	1	1	1	1	1	1	1	0

4. ANALYSIS POPULATIONS

Population	Definition / Criteria	Analyses Evaluated
All Subjects	
 • Comprise of subjects who receive the dose of study medication. 	
 • Safety/tolerability
Analysis	
 • For DGF related endpoints the 'Analysis Population' (AP) is defined as subjects in the 'All Subjects' population who have been declared to have DGF or have reached 7 days. For other endpoints, the AP is defined as subjects having baseline and at least one post-baseline assessment. 	
 • Efficacy • PD/Biomarker
Per Protocol	
 • Comprised of Analysis Population subjects who are compliant with protocol-specific criteria. Subjects with specified protocol deviations will be excluded per Appendix 1. 	
 • Primary efficacy endpoint
PK	
 • Subjects in the 'All Subjects' population for whom a serum pharmacokinetic sample is obtained and analyzed for GSK1070806. 	
 • PK

NOTE :

- Please refer to Appendix 10: List of Data Displays which details the population to be used for each display being generated.

4.1. Protocol Deviations

- Important protocol deviations (including deviations related to study inclusion/exclusion criteria, conduct of the trial, patient management or patient assessment) will be summarised and listed.
- Important deviations which result in exclusion from the analysis population will also be summarised and listed. (Please refer to [Appendix 1: Protocol Deviation Definitions for Per Protocol Population](#)).
- Protocol deviations will be tracked by the study team throughout the conduct of the study in accordance with the Protocol Deviation Management Plan.
 - Data will be reviewed prior to freezing the database to ensure all important deviations and deviations which may lead to exclusion from the analysis are captured and categorised on the protocol deviations dataset.
 - This dataset will be the basis for the summaries and listings of protocol deviations.
- A separate summary and listing of all inclusion/exclusion criteria deviations will also be provided. This summary will be based on data as recorded on the inclusion/exclusion page of the eCRF.

5. GENERAL CONSIDERATIONS FOR DATA ANALYSES AND DATA HANDLING CONVENTIONS

- There are no planned adjustments made for multiple centres in this study.

Table 1 provides an overview of appendices within the RAP for outlining general considerations for data analyses and data handling conventions.

Table 1 Overview of Appendices

Section	Component
11.1	Appendix 1 : Protocol Deviation Definitions for Per Protocol Population
11.2	Appendix 2: Time and Events
11.3	Appendix 3 : Treatment States and Phases
11.4	Appendix 4 : Data Display Standards & Handling Conventions
11.5	Appendix 5 : Derived and Transformed Data
11.6	Appendix 6 : Premature Withdrawals & Handling of Missing Data
11.7	Appendix 7 : Values of Potential Clinical Importance
Error! Reference source not found.	Error! Reference source not found.: Laboratory A&R (QUEST: LAB) Dataset Details
Error! Reference source not found.	Appendix 1 : Abbreviations
11.10	Appendix 10: List of Data Displays
11.11	Appendix 11: Mock Data Displays

6. STUDY POPULATION ANALYSES

6.1. Planned Analyses Overview

The study population analyses will be based on the “All Subjects” population, unless otherwise specified.

Table 2 provides an overview of the planned study population analyses with full details of data displays being presented in Appendix 11.10: List of Data Displays.

Table 2 Overview of Planned Study Population Analyses

Display Type	Data Display's Generated
--------------	--------------------------

	Figure	Table	Listing
Subject Disposition			
Subject Disposition		Y	
Reasons for Screening Failures		Y	Y
Reasons for Withdrawals		Y	Y
Important Protocol Deviations			Y
Deviations Leading to Exclusions from PP Population			Y
Inclusion and Exclusion Criteria Deviations			Y
Demography (recipient)			
Demographics Characteristics		Y	Y
Race & Racial Combinations		Y	Y
Study Populations		Y	Y ^[1]
Medical Condition & Concomitant Medications			
Medical Conditions (Current/Past)		Y	Y
Concomitant Medication		Y	Y
Virology (recipient)			Y
Donor Kidney Data			
Virology (donor)			Y
Demography (donor)		Y	Y
Characteristics (donor)			Y

NOTES:

1. Listing of subjects excluded from any population will be generated only.

7. PRIMARY STATISTICAL ANALYSES

A summary of the observed DGF rate during the study will be provided. The observed DGF rate will be calculated based on “Analysis” population as the primary analysis and based on “Per Protocol” population as sensitivity analysis.

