Treatment	N	Visit	Planned Relevant Time	n	Mean	S.D	Median	Min	Max
GSK1070806 3 mg/kg	xx	xx	x		XXX.X	XX.XX	XXX.X	XXX	XXX
	xx		x		XXX.X	XX.XX	XXX.X	XXX	XXX
	xx	xx	x		XXX.X	XX.XX	XXX.X	XXX	XXX
	xx		x		XXX.X	XX.XX	XXX.X	XXX	XXX

Example : EFF_T3
Protocol : 204824
Population : All Subjects.

Page 1 of n

Table X
Proportion of Subjects with DGF

	Number of Subjects (%) (N)
Subjects with DGF	XXX (%)

Example : EFF_T4
Protocol : 204824
Population : All Subjects.

Page 1 of n

Table X
Proportion of Subjects with Renal Functional Graft within 7 Days after Transplant

	Number of Subjects (%) (N)
Primary Non DGF	XXX (%)
3 day Functional DGF	XXX (%)
7 day Functional DGF	XXX (%)
3 day Intermediate Graft Function	XXX (%)
7 day Intermediate Graft Function	XXX (%)
3 day Immediate Graft Function	XXX (%)
7 day Immediate Graft Function	XXX (%)

Example : EFF_T5
 Protocol : 204824
 Population : All Subjects

Page 1 of X

Table X
 Summary of Maximum Emergent QTc Values by Category

Baseline (N = xx)				Enhanced Monitoring (N = xx)			
Criteria	N	Mean QTc	SD	Criteria	N	Mean max QTc	SD
QT <= 480 msec	xx	xx.x	xx.xx	QTc > 530 msec	xx	xx.x	xx.xx
				QT (uncorr) > 600 msec	xx	xx.x	xx.xx
Bundle Branch Block with QT <= 500 msec	xx	xx.x	xx.xx	QTc >= 550 msec	xx	xx.x	xx.xx
				QT (uncorr) > 600 msec	xx	xx.x	xx.xx

Note: QTc value could be QTcB or QTcF depends on collected data.

Example : SAFE_L1
 Protocol : 204824
 Population : All Subjects

Page 1 of X

Listing X
Listing of XXX

Treatment	Subj.	Analyte (units)	Visit	Actual Date	Planned Relative Time	Time Sample Taken	Result	Change from Baseline
GSK1070806 3mg/kg	PPD	XXX	DAY 1	PPD	PRE DOSE	9:48	0.9	
			DAY 1		4 Hr	9:48	1.10	0.20
			DAY 29		4 Hr	9:48	2.60	1.70
			DAY 85		4 Hr	9:48	1.10	0.20

NOTE: Table adjusted accordingly to the study data.

Example : SAFE_L2
Protocol : 204824
Population : All Subjects

Page 1 of X

Listing X
Listing of Patients Hospitalization and Re-hospitalization Stay

Subject	Age/Gender	Race	DGF (Y/N)	Hosp. Date	Discharge Date	Length of Stay (Day)
XXXXXXX	XX/X	XX	X	XX/XX/XXXX	XX/XX/XXXX	XX
				XX/XX/XXXX	XX/XX/XXXX	XX
XXXXXXX	XX/X	XX	X	XX/XX/XXXX	XX/XX/XXXX	XX

Example : SAFE_L3
Protocol : 204824
Population : All Subjects

Page 1 of X

Table X
Listing of Donor Virology

Subject	Age/Gender	Race	Virology Type	Positive (yes/no)
XXXXXXX	XX/X	XX	Hepatitis B	
			Hepatitis C	
			HIV	
			EBV	

CONFIDENTIAL

204824

Example : SAFE_L4
Protocol : 204824
Population : All Subjects

Page 1 of X

Table X

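### The primary result is the raw DGF rate at stopping, unadjusted for a look after every subject, and neither Section 7 nor its table shell carries the promised posterior or any interval.

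*SAP*

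**What the plan says.** Section 7 is short. It opens: "A summary of the observed DGF rate during the study will be provided". It then settles the status of that rate: "The observed DGF rate will be calculated based on “Analysis” population as the primary analysis", with the Per Protocol population as sensitivity analysis. It names no interval, no posterior quantity and no allowance for the sequential looks.

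Section 3.1.1 describes those looks: "This will start with the first 6 subjects and then with addition of data from each subsequent subject that completes 7 days of the trial". Predictive probability (PP) above 92% supports a Go, below 2% a No-Go, and otherwise the trial continues to at most 30 subjects. Section 2.4 ties the rule to the null: "Stopping rules have been defined to test whether the DGF rate is less than or equal to the null hypothesis rate of 50"%. The synopsis gives two figures for the Go "decision of 0.139 when the GSK1070806 DGF rate is 50% and 0.69 at what has been considered" worthwhile. It describes that second rate as "clinically impactful GSK1070806 DGF rate of 35"%.

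The synopsis (Primary Analyses row) and Section 3.2 promise one thing more: "The posterior probability that the proportion of subjects experiencing DGF is less than 50% will be calculated". Tables 2.01 and 2.02 in the display list use shell EFF_T3, titled "Proportion of Subjects with DGF", which has one row for a count and a percentage. No other listed display carries the posterior.

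**The concern.** A trial that can stop when the running proportion is low (Go) or high (No-Go) tends to end at a chance extreme. The proportion at stopping is then a biased estimate of the true rate, and after a Go it is biased in the drug's favour. A count and percentage alone give the reader neither the size of that effect nor the uncertainty around the rate.

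The SAP says that the analysis after the last patient's day 7 serves internal decision making. The DGF rate is the primary endpoint of a single-arm pilot, so it is the figure most likely to be carried forward. Separately, the SAP disagrees with itself: two places promise a posterior probability as part of the primary result, while the section and tables that should deliver it do not mention it.

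**Working it through.** **Inputs.** Looks at n = 6 to 30, Go if PP > 0.92, No-Go if PP < 0.02 (Section 3.1.1). Figure 1 gives the PP grid; its last row makes success at n = 30 equal to 11 or fewer events. The SAP does not print the prior. A beta-binomial PP with a Beta(5,8) prior recovers the grid (largest difference 0.0005 over the nine rows checked), so Beta(5,8) is an inference used here.

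**Step 1: reproduce the SAP's figures.** PP(n, x) = P(at most 11 − x events in the remaining 30 − n), beta-binomial with parameters 5 + x and 8 + n − x. Exact enumeration over all (n, x) paths, stopping at the first crossing:

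| Rule | P(Go) at 50% | P(Go) at 35% |
|---|---|---|
| SAP, stated | 0.139 | 0.69 |
| Early Go and early No-Go | 0.1389 | 0.6895 |
| Early No-Go only | 0.098 | 0.649 |
| Single look at n = 30 | 0.100 | 0.655 |

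Only the rule with an early Go matches. The SAP's operating characteristics therefore assume it.

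**Step 2: mean of the raw rate.** For each stopping cell, P(cell) = (number of admissible paths) × p^x × (1 − p)^(n − x). The mean raw rate is the sum of P(cell) × x/n, taken over all cells, or over Go cells and divided by P(Go).

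| True rate | All outcomes | Bias | After a Go |
|---|---|---|---|
| 35% | 31.6% | −3.4 | 23.2% |
| 40% (this review's scenario) | 38.8% | −1.2 | 24.3% |
| 50% | 53.2% | +3.2 | 24.1% |

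**Step 3: how much of the Go gap is early stopping?** With one look at n = 30, success alone gives 30.0% at a true 35% and 33.9% at 50%. At 35% the gap of 11.8 points (35 − 23.2) thus splits into 5.0 from conditioning on success (35 − 30.0) and 6.8 from early stopping (30.0 − 23.2).

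**Step 4: sensitivity at a true 35%.** Adding k subjects after the crossing replaces x/n by (x + 0.35k)/(n + k), capped at 30 subjects. The Go average becomes 25.3% with 2 extra, 26.7% with 4 and 30.7% if run to 30. Starting the looks at 8 or 10 subjects gives 24.3% or 25.0%.

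**Step 5: cell by cell.** The path-count (minimum-variance unbiased) estimate is the number of admissible paths to a cell that begin with an event, divided by all admissible paths to it. Its mean over all outcomes is 0.350 and 0.500 at those true rates.

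| Go cell | Raw | Path-count |
|---|---|---|
| 0/6 | 0% | 0/1 = 0% |
| 1/9 | 11.1% | 1/6 = 16.7% |
| 5/19 | 26.3% | 1,206/3,427 = 35.2% |
| 7/23 | 30.4% | 30,454/79,503 = 38.3% |
| 11/30 | 36.7% | 8,776,432/21,071,776 = 41.7% |

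The raw rate lies below the path-count value at every Go cell except 0/6, where both are zero.

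**Step 6: what the display omits.** At 11/30, still a Go, the posterior is Beta(5 + 11, 8 + 19) = Beta(16, 27). P(DGF < 50%) is 0.956 and the 95% credible interval runs from 23.6% to 52.0%. EFF_T3 would show only 11 (36.7%).

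**Step 7: the replacements under the same conditioning.** After a Go, at true 35% / 40% / 50%, the path-count estimate averages 29.4 / 30.6 / 30.2% and the posterior mean 31.4 / 31.8 / 31.9%.

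**The case against.** - **The tempting headline fails.** A reader might infer from the 23.2% and 24.1% that the raw rate hides an inert drug and that a better estimator would expose it. Step 7 shows otherwise: the adjusted and posterior estimates are as flat after a Go. The flatness comes from conditioning on the same few Go cells, not from using a proportion. This objection stands in full.
- **Bias over all outcomes is modest**, about 3 points either way, and part of the gap after a Go is ordinary selection on success. This stands, and the point is sized accordingly.
- **A hard stop is assumed.** Section 3.1.1 says that the trial may be stopped for a No-Go and that a conclusion may be drawn for a Go; it does not say that enrolment ends. Outcomes take seven days, so subjects already enrolled can add data. This stands as a qualifier. Step 4 shows the gap shrinking, but even at 30 subjects the Go average stays below 35%.
- **A posterior is planned.** A reader might infer from Section 7 that there is none; the synopsis and Section 3.2 say otherwise. The gap is one of delivery. EFF_T3 is also an example shell, shared with Tables 2.09 and 2.24, which softens the omission from the shell but does not explain the one from Section 7.
- **The Go decision is untouched.** It rests on predictive probability, not on the raw rate. This stands: the point concerns estimation and reporting only.
- **A descriptive n/N is usual in a pilot.** It is, and it should stay. That does not justify giving it as the only primary estimate, with no measure of uncertainty, after sequential stopping.

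**Conclusion.** The point holds at the level of should-fix. Section 7 as written reports a rate affected by the stopping rule, with no interval, and leaves out a posterior probability that the SAP promises twice. Under stopping at the first crossing, the bias over all outcomes is −3.4 points at a true 35% and +3.2 at a true 50%. After a Go at a true 35% the average is 23.2%, rising to 26.7% with four extra subjects and 30.7% if run to 30.

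These figures rest on the inferred Beta(5,8) prior, looks starting at exactly six subjects, and enrolment ending at the first crossing. The first and last are supported by the match to Figure 1 and to 0.139 and 0.69. The missing posterior and interval need no such assumption. The documents do not support a claim that the primary analysis makes the trial uninterpretable, or that re-estimation restores discrimination after a Go.

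**What to change.** In Section 7, and in the shell used for Tables 2.01 and 2.02:

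1. Keep n/N and label it as the rate at stopping, not adjusted for sequential looks.
2. Add P(DGF < 50%), as Section 3.2 already promises, and the posterior median with a 95% credible interval.
3. Print the design prior in the SAP. Beta(5,8) recovers Figure 1; the sponsor should confirm it.
4. After an early stop, quote the posterior estimate as the effect estimate, supported by a stopping-adjusted one such as the path-count estimate. Both are worth showing: the posterior is pulled towards the prior mean of 5/13 = 38.5%, while the path-count estimate is unbiased over all outcomes only if the stopping rule was followed.
5. State that none of these estimates separates 35% from 50% once a Go has occurred.

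Give these tables their own shell, since EFF_T3 also serves Tables 2.09 and 2.24. The cost is SAP wording, one shell and a short program, with no new data and no change to conduct, settled before database freeze. The downside for the sponsor is a less favourable reported rate after a typical Go.
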